The scale-up of DAA treatment is essential to achieve HCV targets, but this is a huge public health challenge. A major obstacle is under-diagnosis; only 20% of people with HCV worldwide have been diagnosed (6), and only 1% of infected people have received treatment worldwide. The effectiveness of governments and their partners in designing and implementing effective screening strategies to identify the "missing millions" will be a critical determinant of the speed with which elimination can be achieved (8).

Despite the effectiveness of DAAs and that in Colombia they are covered by the health system, the main obstacle to achieving the goal of hepatitis C elimination is under-diagnosis. Among the barriers to timely diagnosis are lack of knowledge on the part of health professionals, availability and access to screening tests, as well as stigma and discrimination, as a country it is required to directly address these barriers to advance in the goals of elimination of viral hepatitis (9). Simplifying the HCV care cascade, ideally across all steps of the continuum of care, would help ensure that more patients remain engaged in the care pathway and ultimately achieve WHO goals (10).

In Colombia, according to SIVIGILA, an average of 228 cases of hepatitis C were reported per year in the period between 2011 and 2016, starting in 2017 there was a significant increase with the notification of 571 cases and continued increase in 2018 (886 cases) and 2019 (897 cases) (11), in 2020 (473 cases) and in 2021 (878 cases), which represent an incidence of 1.70 per 100,000 inhabitants (9).

In 2017, the centralized drug purchasing strategy for the treatment of chronic hepatitis C was implemented, in compliance with Resolution 1692, as part of the effort to eradicate viral hepatitis from the country. The strategy is to purchase Direct Action Antiviral (DAA) drugs directly from the Ministry of Health and Social Protection (MSPS) to guarantee access and reduce treatment costs. When Resolution 1692 of 2017 was issued, the strategy was applied only to people diagnosed with chronic hepatitis C in the contributory regime; however, since January 2020, access to centralized purchasing by the subsidized regime was achieved (12).

According to information from the High-Cost Account (CAC for its acronym in Spanish), between January 1st and December 31st, 2021, 962 persons with the infection were identified in Colombia (13). According to the probable mechanism of transmission, the highest proportions are sexual transmission (72.1%) and parenteral/percutaneous (11.8% of cases) (14). According to information published by the Polaris Observatory up to 2021, there is a prevalence of 0.67% (320,000 cases), 10% of cases have been diagnosed, and of these <1% have been treated and 2639 deaths have been registered annually. According to their predictions with the current behavior, it is estimated that by the year 2051 Colombia will achieve the goals established by the WHO (15).

Three-quarters of HCV-infected people live in low- to middle-income countries, some of

which lack budgets for screening, diagnosis, and treatment campaigns. In 2018, Polaris Observatory reported that only 12 countries were on schedule to meet HCV elimination targets by 2030, these countries were Australia, Egypt, France, Georgia, Iceland, Italy, Japan, Mongolia, the Netherlands, Spain, Switzerland, and the United States (6).

Prevalence studies for HCV have been conducted in less than half of the countries in Latin America, and most of them are of poor-quality design. Extrapolating data from countries with registries, the estimated HCV prevalence rate in Latin America is less than 1%. Estimates made by the Polaris Observatory, according to epidemiological data from the online database in 2019, several countries were able to diagnose a significant percentage of the population with HCV infection; however, only Brazil was able to treat the required number of patients to achieve an annual net cure of more than 1% of those infected (16).

A study modeling the impact of DAA treatment on the course of HCV infection showed that achieving the WHO 2030 targets would require a net cure of 7% per year from 2016. "Net cure" was defined as the number of persons with sustained virologic response, minus new HCV infections, plus HCV-related deaths (17).

The American Association for the Study of Liver Diseases (AASLD), the Infectious Diseases Society of America (IDSA), and the Center for Disease Control (CDC) recommend one-time, routine, opt-out HCV screening for all persons aged 18 years and older. Additionally, (18):

- HCV testing should be performed at least once for all persons with activities, exposures, or conditions or circumstances associated with an increased risk of HCV infection, occasionally testing should be done periodically if risk conditions persist.
- Perform HCV testing for all pregnant women as part of prenatal care.
- Annual HCV testing is recommended for all persons who inject drugs, for HIV-infected men who have unprotected sex with men, and for men who have sex with men taking pre-exposure prophylaxis.

The WHO recommends that in places where the general population has a high seroprevalence of anti-HCV antibodies (defined as a seroprevalence of 2% or higher, or 5% or higher), to provide access to HCV screening tests to all adults and to offer them such tests in linkage with prevention, care and treatment services (2).

To date, no HCV infection prevalence studies have been conducted in the general

population in Colombia, which could represent a drawback for decision-making for the control and elimination of HCV infection. However, studies in blood donors and populations with and without risk factors provide important data to know the overall situation of HCV infection in the country, and modeling analysis has contributed to the strategy in the country (Decree No. 1692 of 2017) (11). For Colombia, it is expected that approximately 409,000 people will have the infection in 2030 (9).

In Colombia, the Ministry of Health and Social Protection established in 2018 the National Response Plan for STIs, HIV, TB/HIV coinfection, and hepatitis B and C 2018-2021. In 2018, the clinical practice guideline for the diagnosis and treatment of hepatitis C infection was updated (14), likewise, progress has been made in the implementation of financing strategies for DAAs, however, it is still pending to improve screening strategies that do not only focus on risk factors and at the same time have generic treatment options available (9).

The country's achievements and challenges in hepatitis C correspond to (13):

- Timely identification of persons who have contracted the infection, so that they can quickly access treatment with direct-acting antivirals (DAAs).
- Maintain the decrease in treatment initiation time and effectiveness above 95%, which translates into a higher rate of cure of the disease.
- Staging for liver fibrosis to all patients at the time of diagnosis and decrease the progression of the disease to advanced stages.
- Continue working on decreasing the progression of fibrosis, liver cirrhosis, hepatocellular cancer, and virus transmission.

Through this observational, multicenter, hospital population study, the prevalence will be determined by screening patients with risk factors for hepatitis C by rapid antibody test, to subsequently perform confirmation with viral load PCR in those seropositive. In addition, support will be provided to patients to facilitate their treatment adherence.

The benefits would be related to raising awareness of the importance of the active search for these patients, reducing the health impact for the screened population, incorporating these strategies in the country's hospital institutions, and obtaining epidemiological information that helps to understand the magnitude of the disease and the opportunity for its elimination.

2 Theoretical framework and state-of-the-art

In 2016, the World Health Assembly endorsed the elimination of viral hepatitis as a public health threat by 2030. WHO-recommended interventions are childhood immunization against hepatitis B, prevention of mother-to-child transmission of hepatitis B virus (HBV) through timely vaccination at birth against hepatitis B and other approaches, safe transfusions, harm reduction for people who inject drugs, and HBV and hepatitis C virus (HCV) testing and treatment (19). Since then, tremendous efforts have been underway to accelerate countries' progress toward HCV elimination through data collection, predictive modeling, and screening and treatment linkage projects (20).

In May 2022, the 75th World Health Assembly took note of a set of comprehensive global health sector strategies against HIV, viral hepatitis, and sexually transmitted infections for the period 2022-2030. Building on the 2016 and new Assembly strategies, some Member States have developed comprehensive national hepatitis programs. To achieve the global viral hepatitis targets under the 2030 Agenda for Sustainable Development, the areas that should be worked on are a. raising awareness, promoting partnerships, and mobilizing resources for diagnosis and linkage to treatment; b. formulating evidence-based policies and compiling data for action; c. improving health equity in the hepatitis response; d. preventing transmission; and e. expanding screening, care, and treatment services (2).

Chronic HCV infection can remain asymptomatic until the late stages, leading to low awareness of the patient's infection status and a significant proportion of undiagnosed individuals (21). HCV infection is diagnosed in two stages: a. Detection of anti-HCV antibodies with a serological test reveals infection. b. If the test is positive for anti-HCV antibodies, a nucleic acid test for HCV ribonucleic acid (RNA) (viral load) is needed to confirm chronic infection and the need for treatment (2).

A study presented at the American Association for the Study of Liver Diseases (AASLD) Annual Meeting has concluded that the prevalence of viremic hepatitis C virus (HCV) infections declined from 66 million in early 2015 to 59 million in early 2020 (22); hepatitis C is a curable disease that if not diagnosed and treated on time can progress to liver cirrhosis, hepatocellular carcinoma, and death related to these and other hepatic or extrahepatic problems (20). The worldwide prevalence of HCV infection is estimated to be 0.75% (95% CI 0.6-0.8%) in the early 2020s (22).

Researchers at the Center for Disease Analysis Foundation (CDA) estimated from 2015 to 2019 7.5 million new chronic HCV infections, 1.3 million newly diagnosed that year (22). By 2019, of the 59 million HCV-infected persons worldwide, an estimated 21% (15.2 million) were diagnosed and, by the end of 2019, 9.4 million had been treated with Direct-Acting Antivirals (DAAs) (62% of persons diagnosed with chronic HCV infection), 8.8 million infections cured, and 5.5 million all-cause and liver-related deaths (2, 22).

Globally, more than three-quarters of HCV viremic infections remained undiagnosed at the beginning of 2020, and more than 90% of people with active hepatitis C remained untreated with DAAs. In high-income countries in 2020, ADC researchers estimated that 6 million people had a viral infection, of whom 47% had been diagnosed and 11% of those diagnosed were receiving treatment. The percentage of people with active hepatitis C is estimated to be 27% in upper-middle-income countries, 15% in lower-middle-income countries, and 16% in low-income countries. As for the percentage of people diagnosed and treated with DAAs, it is 3 % in upper-middle-income countries, 4 % in lower-middle-income countries, and 4 % in low-income countries (23).

In conclusion, the investigators note that DAA treatment is highly concentrated in a few countries, and low diagnosis rates and lack of large-scale HCV screening programs remain barriers to liver virus clearance. Despite the decrease in the number of cases versus 2015, these data suggest that currently, the world is still far from meeting global elimination targets by 2030 (23).

Scaling up interventions for hepatitis screening and treatment from baseline to elimination targets, within the perspective of universal health coverage and in the context of the Sustainable Development Goals entails an additional 1.5% investment, but the effect is proportionally larger, leading to about a 5% reduction in mortality and a 10% increase in healthy life years (19).

The recent WHO global health sector strategy sets new actions and targets to eliminate viral hepatitis by 2030 by reducing new infections to 90% and deaths to 65%, i.e., to half a million each worldwide. For this to happen, care must be more accessible to more people in need. The recommendations given have the potential to substantially expand access to testing and treatment in low- and middle-income countries. The 3 new key recommendations include (3): a. Simplified service delivery and task sharing: testing, care, and treatment of

persons with chronic hepatitis C infection can be provided by non-specialist trained physicians and nurses so that care can be delivered in primary care facilities, harm reduction services, and prisons, which is more accessible and convenient for patients. b. More efficient and simplified hepatitis diagnostics: use of HCV ribonucleic acid (RNA) assays at the point-of-care (POC) as an additional approach alongside laboratory-based RNA assays to diagnose infection. Especially applicable to marginalized populations, such as people who inject drugs, and hard-to-reach communities with limited access to care and high rates of loss to follow-up. c. Harmonized and simplified hepatitis treatment (3).

For testing in all settings, WHO recommends testing focused on persons with signs and symptoms of chronic liver disease and groups with a high prevalence of HCV infection. However, if the prevalence of infection in the general population exceeds 2-5%, WHO recommends testing in the general population (19). WHO recommends treatment with pangenotypic direct-acting antivirals (DAAs) for all adults with chronic hepatitis C infection. In Colombia, according to data from the high-cost account, the currently available DAA sofosbuvir/velpatasvir achieves an efficacy of 98.7% of HCV-infected patients, and a treatment duration of 12 weeks (9).

Early diagnosis of infection and linkage to treatment is one of the priority lines of action. Policies on HCV screening should be articulated in different settings (24). Key issues impeding HCV elimination are the lack of reliable and up-to-date estimates of active HCV infections and related disease burden (21).

The WHO strategy defines ambitious targets to eliminate HCV as a public health threat by 2030, to achieve which the scale-up of DAA treatment is essential, but this is a huge public health challenge. Identification of patients who are unaware of their HCV status represents the main barrier to be overcome, by 2017 according to WHO report only 20% of people with HCV worldwide had been diagnosed (6). Micro-elimination strategies targeting small fractions of the population, as opposed to nationwide elimination programs, have shown improvement in diagnosis and treatment rates resulting in great benefits in expanding the HCV care cascade and achieving WHO targets (21).

According to the epidemiological situation of HCV infection in the general population and the most affected populations, and of the hepatitis C approach plans, the clinical guidelines of countries such as Spain, United Kingdom, Germany, France, Ireland, Canada or Australia

recommend population and opportunistic screening, i.e. HCV screening of persons with exposures and risk situations for infection such as injecting and/or inhaled drug use, risky sexual intercourse, HIV/HBV co-infection, cosmetic procedures performed with sharps without proper safety precautions, admission to correctional facilities (24), anyone who received blood transfusions before HCV serological testing of blood donors was initiated, who received medical or dental interventions in health care settings with substandard infection control practices (25).

The indications for HCV screening by risk exposures instead of population screening allow focusing efforts and resources, responding to the principle of equity in the design, implementation, and evaluation of HCV screening programs in different territories, which allows addressing the barriers to access and use of services in each context (24). Targeted screening would identify a high rate of infected subjects, due to the higher rate of infection related to risk factors, and simultaneously reduce viral transmission by allowing HCV to be eliminated from individuals at higher risk of spreading the infection (26).

The results of the study by Rosato, et al (2022) indicate that opportunistic hospital screening in patients with various comorbidities is a feasible strategy to diagnose and then easily link infected patients to care. They also clearly show the need for increased awareness among general practitioners and other health care specialists, who care for patients with different comorbidities, to address HCV disease management. This is also important because HCV eradication has been shown to significantly improve not only liver disease outcomes but also various comorbidities, such as cryoglobulinemic vasculitis, diabetes, cardiovascular and renal diseases, etc. (27).

Care cascade monitoring (CoC) is an important component of the response to the global hepatitis C virus (HCV) epidemic. The function of a CoC is to represent how many members of a population have progressed through each stage in a sequence of stages required for effective disease control: e.g., diagnosis, treatment, and cure; the findings obtained will enable health system decision-makers to determine where the greatest gaps are in testing, linkage to care, and treatment among persons with chronic HCV infection (28).

A hospital-centered HCV micro-elimination approach provides a framework for expanding linkages to care and treatment on the path to achieving WHO's 2030 targets (21). It is less complex and costly than large-scale national efforts to eliminate HCV, and it can build

momentum by producing small victories that inspire more ambitious efforts (6). Fragile populations require dedicated screening and integrated care programs, which can begin in hospitals and continue in a network involving all processes including telehealth (21), promoting the adoption of new models of care in specific populations (6).

Micro-elimination approaches in populations at high risk for HCV transmission can potentially contribute to "treatment as prevention." The concept of treatment as prevention is to successfully treat an HCV-infected person at risk of transmitting HCV to others and eliminate the possibility of further transmission, thus achieving "prevention." While there is not yet a real-world demonstration of the potency of treatment as prevention, the model indicates that carrying out this strategy on a sufficiently large scale accelerates progression toward population elimination. The goal of treatment as prevention is to successfully treat enough people to reach a threshold at which new infections are significantly reduced. Because of the potential to prevent more infections, many of whom would incur the high costs of treating end-stage liver disease (6).

Targeting those at the highest risk for disease may generate broader community benefits and long-term cost-effectiveness. In support of this approach to HCV eradication, modeling studies by Martin and colleagues (2011 and 2013) have indicated that chronic HCV prevalence could be reduced by treating those at risk for ongoing HCV transmission (29).

The scale-up of HCV treatment is largely dependent on the availability and affordability of diagnostics and drugs. A large portion of the costs is attributable to testing because screening large numbers of people is required to identify 90% of those infected in low-prevalence settings (19).

Since 2017, in Colombia, the High-Cost Account (CAC) has been following up on cases identified with chronic hepatitis C infection, in compliance with the provisions of Resolution 1692 of 2017, which is part of the centralized negotiation and purchase strategy for direct-acting antivirals (30).

According to the Follow-up report on cases with chronic hepatitis C under the centralized drug negotiation and purchase strategy - Cut-off June 30, 2020, in follow-up by the EPS on compliance with what is contemplated in the clinical pathway for the treatment of chronic hepatitis C, 634 cases and 326 cases were reported in the 2019 and 2020 cohort, respectively, for a total of 2,102 patients with a diagnosis of chronic hepatitis C reported to

the high-cost account (including those in the 2017-2018 cohort). Of the 634 users enrolled in the 2019 cohort, 584 initiated treatments, of which 97.6% (570) did so with centrally purchased drugs. Of the 326 cases included in the 2020 cohort, 219 initiated treatments, 98.6% (216) with centrally purchased drugs, which made evident the almost exclusive use of the strategy, except in cases of stage 4-5 chronic kidney disease. Of the 1,142 patients reported to the CAC in 2017 and 2018, 1,079 had initiated treatment and of these 84.2% (n=909), were included in the centralized purchasing model, the most frequently used treatment in 98.2% of cases in the 2019-2020-2021 cohort was sofosbuvir/velpatasvir, reaching 98.77 in 2021 (12).

Regarding the effectiveness of the treatment, it was found that for the 2017-2018 cohort, with centrally purchased drugs, the effectiveness was 95.1% and with drugs outside the centralized purchasing model it was 96.4%. For the 2019 cohort, the effectiveness was 98% and 100% respectively. In the 2020 cohort, treatment effectiveness is at 100% (12).

The report concludes that there is high effectiveness of direct-acting antiviral treatments (greater than 95%), follow-up is observed in the application of the clinical route and practically exclusive use of drugs included in the centralized purchasing model; however, there is a need to encourage screening in the population over 50 years of age and according to risk exposure, as established in resolution 3280 of 2018 (12).

3 Research question

What is the prevalence of HCV in the population with risk factors for hepatitis C virus infection captured by screening with rapid tests in health care institutions in Colombia?

4 Objectives

4.1 General objective

To determine the prevalence of HCV in patients with risk factors for HCV captured through opportunity screening in the hospital institutions included.

4.2 Specific objectives

- Characterize the study population socio-demographically.
- Describe the epidemiological characteristics of HCV antibody-positive patients.

- Determine the proportion of patients with positive HCV antibodies and positive viral load (quantitative) for HCV.
- Perform an exploratory analysis of the association of positive cases and the different risk factors for HCV infection.
- Quantify how many HCV-positive individuals were able to access the management pathway and treatment.

5 Methodology

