	Inhaled or intranasal drug use	Having consumed inhaled drugs at any time.	0. No 1. Yes	Nominal, dichotomous
	Men who have sex with men	Man who has had sex with men.	0. No 1. Yes	Nominal, dichotomous
	Known hepatitis B virus infection	Refer to have a diagnosis of hepatitis B virus.	0. No 1. Yes	Nominal, dichotomous
	Known HIV infection	Refer to HIV diagnosis.	0. No 1. Yes	Nominal, dichotomous
	People who have had tattoos, body piercings, scarification, etc.	Presence of tattoos or piercing or scarification.	0. No 1. Yes	Nominal, dichotomous
	Population deprived of liberty or previously incarcerated persons	Being or having been deprived of liberty in a penitentiary center.	0. No 1. Yes	Nominal, dichotomous
	Liver disorders or disease	A person with abnormal liver	0. No 1. Yes	Nominal, dichotomous

Category	Variable name	Conceptual definition	Operational definition	Measuring scale
		tests or liver disease.		
	Occupational exposure	Healthcare workers or members of public safety (e.g., correctional service officers or police) who have been in contact with blood at work through needlestick or sharps injuries.	0. No 1. Yes	Nominal, dichotomous
	Hemodialysis	A person who has undergone hemodialysis.	0. No 1. Yes	Nominal, dichotomous
	Comorbidities potentially associated with HCV infection.	Diabetes, Ischemic heart disease, Cryoglobulinemia, Chronic renal failure, Sjögren's syndrome, Hypothyroidism, Flat lichen, Rheumatoid arthritis, Non-Hodgkin's lymphoma, Acute lymphoblastic leukemia, Waldenstrom's macroglobulinemia, Chronic renal insufficiency, Sjögren's syndrome	0. No 1. Yes	Nominal, dichotomous
Missed opportunity	Doctor visits	Doctor visits in the last month	How many?	Continued
Sample results	HCV antibody screening test	Report of HCV antibody test result.	0. Non-reactive 1. Reactive	Nominal, dichotomous
	Viral load test	Report the viral load result of those patients who presented reactive HCV antibodies.	0. Non-reactive 1. Reactive	Nominal, dichotomous

Category	Variable name	Conceptual definition	Operational definition	Measuring scale
Follow-up	SIVIGILA Report	The confirmed cases of HCV as a public health event are reported to the surveillance system utilizing form 340.	0: Not reported 1: If reported	Nominal, dichotomous
	Follow-up of confirmed case	Follow-up that each case confirmed in the study has access to consultation by a clinical specialist.	0. No Why? 1. Yes	Nominal, dichotomous

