		Monitoring patient access to treatment	0. No Why? 1. Yes	Nominal, dichotomous

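### Treatment access is recorded as Yes/No without event dates or a stated follow-up window, so a case confirmed late can count as untreated only because too little time has passed

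*Combined protocol and SAP*

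**What the plan says.** The last specific objective in section 4.2 is to "Quantify how many HCV-positive individuals were able to access the management pathway and treatment". Section 7 lists the matching indicator, the share of people diagnosed with chronic hepatitis C who began treatment. Neither gives a time frame.

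Table 1 in section 5.5 has two follow-up items for confirmed cases, "Follow-up that each case confirmed in the study has access to consultation by a clinical specialist" and "Monitoring patient access to treatment". Each is coded 0 (No, with a prompt for the reason) or 1 (Yes). Annex 1 repeats them as tick boxes with an open reason. Apart from the year of a past transfusion, the only date on the form is a completion date at its end, which is not defined or tied to any event.

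The rest of the plan bears on timing as follows:

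- Section 5.1 describes a cross-sectional study.
- Section 5.7 enrols consecutively until the sample size is reached.
- Section 5.9 hands later follow-up to the patient's insurer and promises weekly data review, quarterly reports and a final report.
- Section 5.10 plans frequencies and percentages, with chi-square tests for associations with antibody positivity.
- No section available for this review states when treatment status is read or how a case still in process is counted.

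The opening pages and part of the text between the headings of sections 9 and 12 were not available, so a timetable there cannot be excluded.

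**The concern.** Access to treatment happens after confirmation, so a Yes/No answer means little without knowing how long the patient has been observed. Patients confirmed at the end of recruitment have the least time to reach a specialist and begin treatment. If status is read soon after the last confirmations, some of them will be coded No and begin treatment later. The coded answer does not separate them from patients who were refused, lost or never referred.

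The reported proportion then mixes two things: how well the pathway works, and how long before the data cut each case was confirmed. As a measure of eventual access, the error runs in one direction, downward. Comparisons between hospitals would also be disturbed if sites finish recruiting at different times.

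This is more than a detail that the analysis plan could supply later. Event dates that are not collected cannot be created at analysis, and recovering them would depend on laboratory, notification or insurer records that the plan does not say it will link.

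**Working it through.** **1. What the form can and cannot yield.** To separate lack of access from lack of time, one needs for each confirmed case the date of the RNA result, the date of treatment start if any, and the date on which status was last checked.

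| Needed | Table 1, section 5.5 | Annex 1 |
|---|---|---|
| RNA result | result only | result only |
| Specialist visit | Yes/No and reason | Yes/No and reason |
| Treatment start | Yes/No and reason | Yes/No and reason |
| Last status check | none | none, unless the completion date is meant for this |

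Even if the completion date were the status date, the time elapsed since confirmation would be unknown, because the RNA result has no date.

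**2. The plan's own sample-size figure.** Inputs from section 5.8: N = 280,186, p = 0.5, d = 0.05, design effect 3, 95% confidence (z = 1.96).

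n = 3 × N × p(1−p) / [(d²/z²)(N−1) + p(1−p)]

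- Numerator: 3 × 280,186 × 0.25 = 210,139.5
- Denominator: (0.0025/3.8415) × 280,185 + 0.25 = 182.59
- n = 1,150.86, rounded up to 1,151 as stated

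The same formula at 99.99% confidence gives 4,517 against the stated 4,519, a negligible difference. Section 5.8 gives these as the minimum and maximum per institution. Table 1 of section 5.5 and Annex 1 list seven institutions.

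**3. Scale per case.** Assumptions:

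- All seven sites reach the same number screened.
- The proportion with confirmed infection is 0.67% (the background section reports that "there is a prevalence of 0.67% (320,000 cases" for the country) or 2% (assumed, because section 5.8 says the prevalence in this population is unknown).

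Confirmed cases = number screened × prevalence. One pending case that is coded No and later starts treatment lowers the proportion by 100 / cases points.

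| Screened | Prevalence | Cases | Points per case |
|---|---|---|---|
| 7 × 1,151 = 8,057 | 0.67% | 54 | 1.9 |
| 8,057 | 2% | 161 | 0.6 |
| 7 × 4,519 = 31,633 | 0.67% | 212 | 0.5 |
| 31,633 | 2% | 633 | 0.2 |

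**4. What cannot be computed.** The total loss is the number of such cases times the points per case. That number depends on the recruitment period, the delay from RNA result to treatment, and when status is read. The available sections give none of the three. If the last status check comes later than the longest delay, the number is zero.

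**The case against.** The best defence has four parts.

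- **A timetable may exist in text not seen here.** This stands. Such a timetable could set a late status check and remove the bias. It would not add the missing date fields to Table 1 or Annex 1.
- **A count at study close is a legitimate descriptive result.** This is partly right. Neither the objective nor the indicator says ever treated, and a status count with its date reported is interpretable. But the plan does not state that date, and without RNA-result dates a reader could not judge how mature the count is.
- **Existing fields soften the problem.** Notification, specialist visit and the open reason can show that a patient is still in process, and the smaller case counts could be hand-coded. This reduces the harm. It depends on someone writing the reason, no code for pending is defined, and the elapsed time is still missing.
- **The delay is not demonstrated.** The resources text before section 12 describes a quarterly download of notified cases by the High Cost Account. It does not say that treatment waits for it, and section 5.9 has study hepatologists guiding patients to the confirmatory test. This stands: delay is plausible, but its length is unknown.

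Three stronger readings are tempting and are not supported.

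- **The background cohorts as a measure of the bias.** The follow-up report cited in section 2 has "Cut-off June 30, 2020" in its title. "Of the 634 users enrolled in the 2019 cohort, 584 initiated treatments" gives 92.1%, and "Of the 326 cases included in the 2020 cohort, 219 initiated treatments" gives 67.2%, a gap of 24.9 points. Short follow-up of the 2020 cohort may explain part of it. However, "since January 2020, access to centralized purchasing by the subsidized regime was achieved", and national notifications fell from 897 in 2019 to 473 in 2020, so the cohorts differ in more than time.
- **Time from PCR to treatment as an outcome the study cannot deliver.** Section 7 names it only as an impact expected 1 to 4 years after the project, and the indicator attached is a number of people treated. No objective requires the interval.
- **The data system as unable to update treatment status.** The security annex lists interface commands and does not describe what the viral-load form contains, so nothing follows from it about follow-up.

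**Conclusion.** The concern holds as a gap in measurement and analysis for one specific objective and its indicator. As written, a case confirmed late can be coded No only because little time has passed, and the form lacks the dates needed to detect or correct this.

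The size cannot be derived from the documents. It is nil if status is read late enough after the last confirmation. Otherwise, each such case costs about 0.2 to 1.9 points, assuming seven sites, 1,151 to 4,519 screened at each, and 0.67% to 2% confirmed infection.

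A reader might infer that the treatment proportion will certainly be too low, or by a stated amount. The documents do not support that, because they give no recruitment length, delay or reading date. The prevalence objective is not affected. The change should be made before data collection, because the dates are simple to record then and may be hard to recover later.

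**What to change.** For antibody-positive patients, add four dates to Table 1 of section 5.5 and to Annex 1: RNA result, first specialist visit, treatment start and last status check. The notification date is optional. Add a response code for pending at the data cut, separate from No, and define what the form's completion date refers to.

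In section 5.10, state the data-cut rule and one of two analyses:

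- the proportion of RNA-positive patients who started treatment within one prespecified window from the RNA result, among those whose full window has elapsed at the data cut. Membership of that group should be set by the RNA-result date, not by whether treatment has begun; or
- a cumulative incidence of treatment start from the RNA result, censored at the last status date.

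If a crude count at study close is also reported, give its date and the number pending.

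The cost is a few fields and one or two sentences. The RNA-positive patients would number about 54 to 633 under the assumptions above; the antibody-positive group is larger by those whose RNA test is negative. The real downside is timing: the final figure is delayed by up to one window, or the last cases are left out or censored.
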